9. DATA HANDLING CONVENTIONS

9.1 PREMATURE WITHDRAWAL AND MISSING DATA

Patients who prematurely discontinue study treatment will be encouraged to remain in the study and continue with all other aspects of the study. Patients who decide to discontinue study treatment

prematurely and not continue with all other aspects of the study will be considered to have withdrawn from the study.

The primary analysis of the primary endpoint will use a mixed-effects model based on restricted maximum likelihood estimation. The assumption will be made that, conditional on fixed and random effects, data are missing at random; therefore no imputation of missing data will be performed. The robustness of the analysis will be evaluated by sensitivity analyses with missing post-baseline values imputed using several imputation algorithms (see 10.2.1.2).

9.2 BASELINE AND CHANGE FROM BASELINE

For all endpoints, the baseline value is defined as the last non-missing value obtained prior to the first dose of study treatment.

For continuous laboratory variables, electrocardiogram (ECG) data and vital signs, if two visits are equally eligible to assess patient status at baseline (e.g., screening and baseline assessments both on the same date prior to first dose with no washout or other intervention in the screening period), the average will be used as the baseline value. In the scenario where there are two assessments on day 1, one with time recorded and the other without time recorded, the one with time recorded will be selected as baseline. Where safety data will be summarized over time, time on study will be calculated in relation to date of first study treatment.

In all summaries, change from baseline variables will be calculated as the post-treatment value minus the value at baseline. The percentage change (relative change) from baseline will be calculated as:

$$100 \times (\text{Post-baseline value} - \text{Baseline value}) / (\text{Baseline value})$$

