3.1.1. Part A: Placebo-Controlled Treatment Period

Part A of Study 1821-FSH-301 is a global, randomized, double-blind, placebo-controlled, parallel-group, multicenter study with a [REDACTED] screening period, a 48-week treatment period, and safety follow-up visits [REDACTED] days and [REDACTED] days after last dose (for patients who discontinue from treatment early or who do not rollover into Part B).

During the placebo-controlled treatment period, a total of approximately 230 patients with FSHD will be randomized 1:1 to receive 15 mg PO of losmapimod (n=115) or placebo (n=115) tablets BID with food for 48 weeks (Figure 1).

Patients will complete a [REDACTED] screening period followed by a 48-week placebo-controlled treatment period. After Week 48 patients will have the option to participate in Part B: Open-Label Extension (Section 3.1.2).

- Patients will have the opportunity to rollover into Part B after completing Part A. Approval from the Medical Monitor will be required if patients do not rollover without interruption after completing the Week 48 assessments. If a patient rolls over more than 7 days after the last dose in Part A, they may be required to repeat selected Week 48 assessments at the discretion of the Medical Monitor.
- For patients who rollover into Part B, the Week 48 visit will be the end of study visit for Part A.
- All patients who discontinue from treatment early or who do not rollover into Part B will return for a complete safety follow-up visit [REDACTED] days after the last dose of study drug and will complete a safety follow-up phone screen [REDACTED] days after the last dose of study drug.

During the treatment period, patients will be asked to attend the study clinic at each scheduled visit (Table 7).

Safety and tolerability will be evaluated based on the assessment of AEs, AEs of special interest (AESIs), SAEs, laboratory tests, ECGs, vital signs, and physical examinations. The full schedule of assessments for the placebo-controlled treatment period is provided in [Table 7](#). Scheduled visits may be split over 2 days, if required, and must be completed within the protocol-defined visit windows ([Table 7](#)). Unscheduled visits may be performed if clinically indicated.

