6.1.1. Reachable Workspace

The RWS Microsoft Kinect-based movement sensor system will be used at the visits noted in [Table 7](#) and [Table 8](#) to determine the patient's RWS.

The RWS is a 3D sensor-based system (using a single depth-ranging sensor) that can unobtrusively detect an individual's RWS and reflects individual global UE function, including shoulder and proximal arm. Previous and ongoing evaluation of the hardware and software system using a commercially available and cost-effective single sensor platform (Microsoft Kinect sensor) has demonstrated its high reliability, repeatability, face validity, feasibility, sensitivity to change, and promise as a COA for FSHD and other neuromuscular disorders ([Han et al. 2015](#)). Moderately impaired individuals with baseline RSA values between 0.20 and 0.70 (out of 1.0, for quadrants Q1-Q4) were more likely to show predictable declines over time with an annualized total RSA loss of 2.74% ($P=0.047$) ([Hatch, Chan, et al. 2019](#)). This study includes an inclusion criteria of screening total RSA (Q1-4) without weight between 0.20 and 0.70 to enrich for a population that is likely to change over a 1-year period.

During the evaluation, patients will be seated in front of the Microsoft Kinect sensor and will undergo a standardized upper extremity movement protocol under the supervision of a study clinical evaluator while looking at a video monitor. The evaluation will be performed with and without weights and on both the dominant and non-dominant arms. The Kinect sensor will track the 3D upper limb trajectory and transform the movements into a body-centric coordinate system. Each individual's RWS envelope will be reconstructed in a graphical output. Each body side's RWS envelope will be divided into 5 quintants, with the shoulder joint serving as the origin. The absolute total RWS surface envelope area (m^2) as well as areas for each of the

quadrants will be calculated. Scaling of the data by each person's arm length will allow normalization for comparison between patients (Han et al. 2015).

Instructions for equipment assembly, setup, testing, and site certification; a manual of operation; and a quick reference guide will be described in an RWS manual. A central reader will be responsible for training, quality control, data analysis, and standardization of the RWS across all sites in the study.

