9.1.3. Sample Size Determination

The target population for this clinical trial is patients with FSHD1 and FSHD2. The clinical trial will reflect the current epidemiologic information about FSHD, with patients with FSHD1 making up approximately 95% of the study population and the other 5% being people living with FSHD2. However, all studies thus far have been conducted with FSHD1 patients; therefore, this calculation was based on that population. Additional FSHD2 patients will be enrolled to explore safety and efficacy in this subgroup.

Assuming the within-group SD of change is 0.08 and that 10% of the study population has missing Week 48 data, a sample size of 210 patients with FSHD1 (105 patients per group) will be needed to provide at least 95% power with a 2-sided test at 0.05 significance level to detect a difference of 0.05 between losmapimod and placebo in change from baseline in average total RSA Q1-Q5 with 500 g wrist weight at Week 48. An additional approximately 20 patients with FSHD2 will be recruited. The primary analysis will include patients with FSHD1 and FSHD2.

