APPENDIX 1. SCHEDULES OF ASSESSMENTS

Table 7: Part A: Placebo-Controlled Treatment Period Schedule of Assessments

Event/Assessment	Screening	Baseline	Week 4	Week 12	Week 24	Week 36	Week 48	ET Visit ^a	Safety F/U █ after last dose of study drug ^b	Safety F/U Phone Screen █ after last dose of study drug ^b
Visit Number	0	1	2	3	4	5	6	-	Variable ^c	Variable ^c
Study Day	█	1	28	84	168	252	336	-	343	373
Visit Window (days) ^d	N/A	±7	±7	±7	±7	±7	±7		±3	±5
Clinic visit	X	X	X	X	X	X	X	X	X	
ICF	X									
Inclusion/ exclusion	X	X								
Demographics	X									
Medical history	X									
Weight ^e	X	X			X		X	X	X	
Height ^e and BMI	X									
Genetic confirmation of FSHD ^f	X									
Randomization		X								
█	█									
Urine drug screen ^h	X									
Vital signs ⁱ	X	X	X	X	X	X	X	X	X	
Standard 12-lead ECG ^j	X	X	X	X	X	X	X	X	X	
Physical examination ^k	X	X	X	X	X	X	X	X	X	
Urinalysis	X	X	X	X	X	X	X	X	X	
Serum FSH ^l	X									
Serum pregnancy test ^m	X									

Event/Assessment	Screening	Baseline	Week 4	Week 12	Week 24	Week 36	Week 48	ET Visit ^a	Safety F/U [REDACTED] after last dose of study drug ^b	Safety F/U Phone Screen [REDACTED] after last dose of study drug ^b
Visit Number	0	1	2	3	4	5	6	-	Variable ^c	Variable ^c
Study Day	[REDACTED]	1	28	84	168	252	336	-	343	373
Visit Window (days) ^d	N/A	±7	±7	±7	±7	±7	±7		±3	±5
Urine pregnancy test ⁿ		X	X	X	X	X	X	X	X	
Hematology	X	X	X	X	X	X	X	X	X	
Serum chemistry ^o	X	X	X	X	X	X	X	X	X	
Serology (HBsAg, HCV, and HIV 1/HIV 2) ^p	X									
PK ^q			X					X	X ^r	
[REDACTED]		[REDACTED]	[REDACTED]					[REDACTED]	[REDACTED]	
RWS	X	X	X	X	X	X	X	X ^r		
Hand-Held Dynamometry		X	X	X	X	X	X	X ^r		
Neuro-QoL UE Function	X	X	X	X	X	X	X	X ^r		
MSK MRI	X				X		X	X ^r		
PGIC			X	X	X	X	X	X ^r		
[REDACTED]			[REDACTED]	[REDACTED]	[REDACTED]	[REDACTED]	[REDACTED]	[REDACTED]	[REDACTED]	
[REDACTED]		[REDACTED]	[REDACTED]							
[REDACTED]		[REDACTED]	[REDACTED]							
[REDACTED]		[REDACTED]			[REDACTED]		[REDACTED]	[REDACTED]	[REDACTED]	
[REDACTED]		[REDACTED]			[REDACTED]		[REDACTED]	[REDACTED]	[REDACTED]	
[REDACTED]		[REDACTED]			[REDACTED]		[REDACTED]	[REDACTED]	[REDACTED]	
[REDACTED]		[REDACTED]			[REDACTED]		[REDACTED]	[REDACTED]	[REDACTED]	
Study drug dispensation		X	X	X	X	X	X			

Event/Assessment	Screening	Baseline	Week 4	Week 12	Week 24	Week 36	Week 48	ET Visit ^a	Safety F/U [REDACTED] after last dose of study drug ^b	Safety F/U Phone Screen [REDACTED] after last dose of study drug ^b
Visit Number	0	1	2	3	4	5	6	-	Variable ^c	Variable ^c

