5. SAMPLE SIZE CONSIDERATIONS

The target population for this clinical trial is patients with FSHD1 and FSHD2. The clinical trial will reflect the current epidemiologic information about FSHD, with patients with FSHD1 making up approximately 95% of the study population and the other 5% being people living with FSHD2.

Assuming the within-group standard deviation (SD) of change is 0.08, a sample size of 210 patients with FSHD1 (105 patients per group) will be needed to provide at least 95% power with a 2-sided t-test at 0.05 significance level to detect a difference of 0.05 between losmapimod and placebo for the primary endpoint. An additional approximately 20 patients with FSHD2 will be recruited. The primary analysis will include patients with FSHD1 and FSHD2. Premature withdrawal and missing data are discussed in 9.1.

For the secondary efficacy endpoints of change from baseline in WB longitudinal composite MFI of B Muscles and PGIC at Week 48, assuming the within-group SDs are 0.72 and 1.0 respectively, a sample size of 210 patients with FSHD1 will provide at least 95% power with a 2-sided t-test at 0.025 significance level to detect a difference of 0.5 and 0.6 respectively between losmapimod and placebo.

For the secondary efficacy endpoint of relative change from baseline in average shoulder abductor strength at Week 48, assuming the within-group SD is 46, a sample size of 210 patients with FSHD1 will provide at least 75% power with a 2-sided Wilcoxon rank-sum test at 0.025 significance level to detect a difference of 20.2 between losmapimod and placebo.

In the above calculations, the assumed treatment differences and SDs are based on results from an ongoing Phase 2 study, Study FIS-002-2019 (ReDUX4). It is also assumed that 10% of the study population has missing Week 48 data. All power calculations were performed using the POWER Procedure of SAS[®] Version 9.4.

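### The primary MMRM uses only the last pre-dose reachable workspace value, although a screening assessment is also scheduled; adding it as a second covariate would give modest extra precision

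*SAP*

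**What the plan says.** Protocol Table 7, repeated in SAP Appendix B, marks RWS at Screening, Baseline and Weeks 4, 12, 24, 36 and 48. Protocol 6.1.1 says of the assessment: "The evaluation will be performed with and without weights and on both the dominant and non-dominant arms". It makes no exception for screening. The only screening score that the protocol names is the eligibility score in 4.1.1.1: Q1-Q4, unweighted, dominant arm, 0.2 to 0.7.

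SAP 9.2 sets the baseline rule: "For all endpoints, the baseline value is defined as the last non-missing value obtained prior to the first dose of study treatment". It allows averaging of pre-dose values only for laboratory, ECG and vital-sign data. SAP 9.3.3.1 lists the RWS values needed for the primary endpoint as baseline and the five later visits; screening is not listed. SAP 8.3.1 and Protocol 9.1.1 and 9.1.6.3 give the MMRM one baseline value and its interaction with visit.

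The sample size (Protocol 9.1.3) rests on this: "Assuming the within-group SD of change is 0.08 and that 10% of the study population has missing Week 48 data". The SAP bases the power on an unadjusted two-sample comparison, claiming to "provide at least 95% power with a 2-sided t-test at 0.05 significance level".

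**The concern.** A single RWS session measures a patient's underlying reach with error. That error weakens the baseline covariate, so the model explains less of the Week 48 variation than it could. A second session before randomisation carries independent information on the same quantity. Treatment cannot affect it, so adding it as a covariate does not bias the treatment comparison or change the estimand.

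What is at stake is the width of the confidence interval, and power if the true effect is smaller than planned. A smaller effect is conceivable. Protocol section 1 cites an annualised RSA loss of 2.74% in patients with baseline RSA of 0.20 to 0.70. In percentage points that is about 0.027 a year; as a relative loss it is at most 0.0274 × 0.70 = 0.019. Halting such a decline completely would yield less than 0.05. That figure is for Q1-Q4, however. The 0.05 comes from the Phase 2 randomised study, where the placebo group fell faster (-7.49% in the dominant arm with weights, Protocol 1.2.4).

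**Working it through.** **1. The plan's own figure.** Inputs from Protocol 9.1.3: SD of change 0.08, difference 0.05, two-sided alpha 0.05, 105 per group, 10% missing. Evaluable per group: 105 × 0.9 = 94.5, taken as 94.

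Power = Φ(Δ / (σ√(2/n)) − 1.96). The standard error is 0.08 × √(2/94) = 0.01167. Then 0.05 / 0.01167 = 4.285, and Φ(4.285 − 1.96) = 99.0% (98.9% with the exact t distribution). The stated floor of 95% is met with room to spare.

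**2. Model for the gain.** Let T be the between-patient SD, e the measurement-error SD of one session, and d the variance of true change. The planned SD of change fixes d: 0.08² = d + 2e². Neither T nor e is in the documents, so e = 0.02 to 0.05 and T = 0.12 to 0.20 are assumptions. The residual variance at Week 48 is:

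- one baseline: e² + d + 1/(1/T² + 1/e²)
- baseline plus screening, equal independent errors: e² + d + 1/(1/T² + 2/e²)
- baseline plus screening, screening error SD 2e: e² + d + 1/(1/T² + 1/e² + 1/(4e²))

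**3. Worked case, e = 0.04, T = 0.15.** e² = 0.0016, d = 0.0064 − 0.0032 = 0.0032, 1/T² = 44.4, 1/e² = 625.

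- One baseline: 0.0048 + 1/669.4 = 0.006294 (SD 0.0793).
- Equal errors: 0.0048 + 1/1294.4 = 0.005573 (SD 0.0746), a cut of 11.5%.
- Noisier screening: 0.0048 + 1/825.7 = 0.006011 (SD 0.0775), a cut of 4.5%.

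**4. Range.** Variance cuts span T = 0.12 to 0.20; power uses T = 0.15 and 94 per group.

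| e | Variance cut, equal errors | Variance cut, screening error 2e | Power at 0.03: one baseline / equal / noisier |
|---|---|---|---|
| 0.02 | 3.0–3.1% | 1.2% | 73.0 / 74.3 / 73.5% |
| 0.03 | 6.5–6.8% | 2.5–2.7% | 73.2 / 76.1 / 74.3% |
| 0.04 | 10.9–11.9% | 4.2–4.7% | 73.6 / 78.7 / 75.6% |
| 0.05 | 16.3–18.2% | 6.2–7.2% | 74.6 / 82.2 / 77.5% |

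At the planned 0.05, power moves from 99.0–99.3% to 99.2–99.8%, a gain of at most 0.7 points.

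**5. Cross-check by correlations.** Let ρ be the correlation of baseline with Week 48, and r that of screening with baseline. With common variance s² = 0.08² / (2(1 − ρ)), the residual variance is s²(1 − ρ²) with one baseline and s²(1 − 2ρ²/(1 + r)) with two equally precise ones. For ρ from 0.70 to 0.95 and r from ρ to 0.98, the cut is 1.0% to 23.7%. It tends to zero as r approaches 1.

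**6. Averaging or two covariates.** A simulation applied the 0.2 to 0.7 screening selection. With equal errors the two forms cut the variance by the same 3% to 16%. With screening error SD twice that of baseline (0.08 against 0.04), averaging raised the residual variance by 5.4%, while two covariates still cut it by 4.3%.

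**The case against.** Taking the last pre-dose value is a standard, unbiased convention, and the documents apply it consistently. A reader might infer that the primary analysis is faulty or the trial underpowered. The documents support neither: the plan claims to "provide at least 95% power with a 2-sided test at 0.05 significance level to detect a difference of 0.05 between losmapimod and placebo", and step 1 gives about 99% without any credit for covariates.

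A reader might also take it as settled that a weighted, two-arm Q1-Q5 score exists at screening. Table 7 shows only a mark per visit. The content follows from the general sentence in Protocol 6.1.1, and operational detail sits in an RWS manual outside these documents. The inference is reasonable, but the sponsor must confirm it.

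The upper end of the gain is easy to over-read. On 230 patients, the equal-error case at e = 0.05 and T = 0.20 equates to 230 × (0.006253 / 0.005112 − 1) ≈ 51 extra patients. It requires measurement error to supply 2 × 0.05² / 0.0064 = 78% of the planned change variance, and equal, independent errors at both visits. A first session may well be noisier, and errors correlated at 0.5 between the two sessions would cut the gain to about 1.5% to 8%. Such a headline is a best case.

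The change is also more than an SAP wording edit, since the protocol lists the model terms and SAP section 11 reports no departures. All of these limits stand. They set the size and wording of the point; none removes it.

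**Conclusion.** The point holds as an optional efficiency improvement. If weighted two-arm screening data exist, a valid pre-randomisation covariate for the primary endpoint has been collected and is not used. Across the assumptions in step 4, the standard error would fall by about 1.5% to 10% with equal independent errors, and by about 0.6% to 4% with a screening session twice as noisy. The practical value is a tighter interval and, if the true difference is nearer 0.025 to 0.03 than 0.05, a few points of power. It is not a reason to doubt the planned primary analysis. The documents give no test-retest figure for RWS, so the gain cannot be stated as one number.

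**What to change.** Before unblinding:

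- Confirm that weighted, two-arm Q1-Q5 data were captured at screening.
- Keep the definitions of baseline and change from baseline in SAP 9.2.
- In SAP 8.3.1 and 10.2.1.1, add screening average total RSA Q1-Q5 with 500 g, and its interaction with visit, as a second covariate in the primary MMRM. Do not average it with baseline.
- If the screening value is missing, set it to the baseline value.
- Extend the blinded RWS validity review in SAP 9.3.3.1, which now covers post-baseline points only, to screening values.
- Carry the term through the sensitivity analyses that reuse the primary model. Allow it to be dropped in small subgroups, such as the roughly 20 FSHD2 patients, where SAP 8.5 already foresees convergence problems.
- Record the departure from Protocol 9.1.1 and 9.1.6.3 in SAP section 11, or amend the protocol.

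Neuro-QoL UE is also scheduled at both visits and analysed by MMRM, so the same term could be added there.

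The cost is about five fixed-effect parameters (one slope at each of five post-baseline visits), which is negligible for 230 patients, plus matching edits to the analysis programs and a declared change of model. No new data are needed.

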9.3 DERIVED AND TRANSFORMED DATA

9.3.1 General derivations

9.3.1.1 Average

Where an average is required, but some data are missing, the average is the mathematical mean of the non-missing value(s).

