4.1.1. Part A: Placebo-Controlled Treatment Period

4.1.1.1. Inclusion Criteria

1. Patient will sign and date an informed consent form (ICF).
2. Patients will have a diagnosis of FSHD1 or FSHD2 verified by genetic testing (see [Section 6.2.1](#)).
 - Randomization will be stratified for FSHD1 to ensure that treatment allocation is balanced across FSHD repeat number categories (ie, 1 to 3 repeats versus 4 to 9 repeats).
 - Randomization will be stratified for FSHD2 to ensure that an equal number of patients will be allocated to treatment and placebo.
3. Patients will have a Clinical Severity Score of 2 to 4 (Ricci score; range 0 to 5) at screening. Patients who are wheelchair-dependent or dependent on walker or wheelchair for activities are not permitted to enroll in the study.
4. Patients with screening total RSA (Q1-Q4) without weight in the dominant UE assessed by RWS ≥ 0.2 and ≤ 0.7 .
5. Willing and able to comply with scheduled visits, treatment plan, study restrictions, laboratory tests, contraceptive guidelines, and other study procedures.
6. No contraindications to MRI.
7. Patients (male and female) will be between the ages of 18 and 65 years at the time of consent, inclusive.
 - A female patient is eligible to participate if she is of non-childbearing potential, defined as pre-menopausal females with a documented hysterectomy, bilateral salpingectomy, or bilateral oophorectomy; if she is postmenopausal, defined as no menses for 12 months without an alternative medical cause; OR

- If of child-bearing potential, she is using a highly effective method for avoidance of pregnancy for the duration of dosing and until 90 days after the last dose. For details regarding contraception requirements, refer to [Section 5.5.1.1](#).
- Male patients must agree to use one of the contraception methods listed in [Section 5.5.1](#). This criterion must be followed from the time of the first dose of study medication and until 90 days after the last dose of study drug.

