9.3.3 Efficacy derivations

9.3.3.1 Primary endpoint

Change from baseline in average total RSA Q1-Q5 with 500 g wrist weight at Week 48, where the average is applied over both arms.

The RWS (total RSA Q1-Q5) measurements required for the analysis of the primary endpoint are those assessed at baseline and at weeks 4, 12, 24, 36 and 48, on both the dominant and non-dominant arms. At each visit the RWS for each arm (Left and Right) is the sum of the 5 RSA measurements: Q1+Q2+Q3+Q4+Q5, where the weight used is 500g. The average total RSA is the average of the two totals:

Average = Mean of (Total for Left Arm with 500g weight, Total for Right Arm with 500g weight)

Change from baseline is derived as specified in 9.2. above.

Note: the average over both arms per visit needs to be calculated before computing changes from baseline.

If an arm is not tested for RWS, and the reason code is W='Weakness related', then the RWS for that arm should be imputed as 0.

Because the RWS data are used in the primary endpoint analysis for this study, Fulcrum or its designated vendor will perform additional cleaning of these data. Fulcrum or its designated vendor will use the following criterion to identify potentially invalid data points: post-baseline data points that show a change (increase or decrease) >50% from the previous result on total RSA Q1-Q5. Records meeting this criterion will be sent to the RWS vendor for further investigation. After blind review, the RWS vendor will communicate to Fulcrum or its designated vendor any records that are deemed invalid because of problems with the software and should therefore not be included in the analysis. These rare sessions, if any, will be flagged by the RWS vendor, and their associated results, including total RSA Q1-Q5, total RSA Q1-Q4, sum of Q1 and Q3, and all 5 individual quadrants, will be removed from the RWS analysis (also see 9.3.3.3).

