9.3.3.2 Secondary endpoints

PGIC at Week 48

PGIC is a single-item rating scale. Patients will be asked to rate their overall status relative to baseline: 1 = Very much improved, 2 = Much improved, 3 = Minimally improved, 4 = No change, 5 = Minimally worse, 6 = Much worse, 7 = Very much worse. The PGIC is measured at weeks 4, 12, 24, 36 and 48. Missing values are treated as missing.

Change from baseline in whole-body (WB) longitudinal composite muscle fat infiltration (MFI) (B muscles) at Week 48

This endpoint is derived for B-muscles as described in 9.3.1.3, where Y=MFI.

Relative change from baseline in average shoulder abductor strength by hand-held quantitative dynamometry at Week 48

Shoulder abductor strength is measured three times on each arm at baseline, weeks 4, 12, 24, 36, and 48, and a mean value is recorded in the EDC. At each timepoint, the average mean for the two arms will be derived, and a relative change of this average from baseline will be derived as specified in 9.2. above.

Missing values will be treated as missing.

[figure not shown]
Change from baseline in Neuro-QoL-UE Function at Week 48

[figure not shown]
The Neuro-QoL-UE is a 20-item questionnaire, from which a single scale is derived. It is measured at baseline and at weeks 4, 12, 24, 36 and 48. The Neuro-QoL-UE measures ability across fine motor and activities of daily living involving digital, manual, and reach-related function and self-care. Responses are divided into 5 ordinal levels (1 = unable to do, 2 = with much difficulty, 3 = with some difficulty, 4 = with a little difficulty, 5 = without any difficulty). The endpoint is derived as:

[figure not shown]
$$20 \times (\text{Sum scores from all items answered}) / (\text{Number of items answered})$$

[figure not shown]
The Neuro-QoL-UE will be recorded as missing if fewer than 10 items are answered. The score ranges from 20-100, with higher scores reflecting better upper extremity fine motor function.

Change from baseline is derived as specified in 9.2. above.

[figure not shown]
Change and relative change from baseline in muscle strength by hand-held quantitative dynamometry

There are eight dynamometry outcomes measured at baseline and at weeks 4, 12, 24, 36 and 48. They relate to 4 assessment areas:

- [1] Average dominant shoulder abductor strength (kg)
- [2] Average non-dominant shoulder abductor strength (kg)
- [3] Average dominant hand grip strength (kg)
- [4] Average non-dominant hand grip strength (kg)

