 - (Step 1) AMRA calculates the Week 24 **Reference Screening** values based on the set of muscles that are still eligible ($SI_{long} = 1$). (Note: if new signal quality issues are identified, the eligible muscle count will change and the Reference Screening values will be updated; otherwise, if the muscle count has not changed, the Reference Screening values at Week 24 remain the same as the initial study-level Reference Screening values at Screening). AMRA also refers to these as **Reference Timepoint 1 (TP1)** values and provides them as a set of 4 results: Reference Screening LMV muscle count, LMV_{tot} , MFI_{tot} , and MFF_{tot} .

- (Step 2) AMRA calculates the **Week 24** actual values based on the same set of muscles eligible at this visit. AMRA also refers to these as **Timepoint 2 (TP2)** values. Note: these TP2 results are interim values that AMRA uses for the calculations but does not directly provide them in the MRI data transfer to Fulcrum (see additional details below in the Section for Post-Data Transfer Processing Steps).
- (Step 3) AMRA derives the **Week 24 Change from Reference Screening** values using the Week 24 TP1 and TP2 values (from Steps 1 and 2 above). AMRA provides these change results in the data transfer as a set of 4 highly derived longitudinal composite results:
 - absolute change in LMV_{tot} (unit = L),
 - relative change in LMV_{tot} (unit = %),
 - absolute change in MFF_{tot} (unit = percentage points),
 - absolute change in MFI_{tot} (unit = percentage points).
- **At Week 48:** AMRA repeats the process (as noted above for Week 24) and provides a similar set of visit-level **Reference Screening** and **Change from Reference Screening** at Week 48 values in the data transfer to Fulcrum. Note: for the Week 48 visit, AMRA also includes an extra set of composites that are calculated using Week 24 as the Reference TP1 instead of Screening. However, for the double-blind placebo-controlled portion of the study, this extra set of Reference Week 24-as-TP1 results will not be used; only Reference Screening TP1-based results will be used for this portion of the study.

Longitudinal Composites: Post-Data Transfer Processing Steps

Once AMRA provides the highly derived longitudinal composite results, Fulcrum will perform some additional post-data transfer processing steps to prepare the longitudinal results for analysis.

Calculate Actual TP2 Analysis Values

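### When one arm's reachable workspace is missing for a reason other than weakness, the primary endpoint subtracts a two-arm baseline from a one-arm value and scores arm asymmetry as change

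*SAP*

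**What the plan says.** Protocol 6.1.1 plans RWS on both sides: "The evaluation will be performed with and without weights and on both the dominant and non-dominant arms". SAP 9.3.3.1 defines the visit value as the mean of the left-arm and right-arm totals with the 500 g weight, and fixes the order of derivation: "Note: the average over both arms per visit needs to be calculated before computing changes from baseline".

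The only arm-level missing-data rule visible for RWS is in the same section. If an arm is untested because of weakness, "then the RWS for that arm should be imputed as 0". An arm missing for any other reason falls under the general rule in SAP 9.3.1.1: "Where an average is required, but some data are missing, the average is the mathematical mean of the non-missing value(s". SAP 9.2 then subtracts baseline, where "the baseline value is defined as the last non-missing value obtained prior to the first dose of study treatment". It sets no condition that the same arms enter both terms.

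For average shoulder abductor strength, SAP 9.3.3.2 averages the two arms, takes the relative change and adds "Missing values will be treated as missing". It does not say whether one arm is enough to form the average.

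**The concern.** Read together, 9.3.1.1, 9.3.3.1 and 9.2 let one arm be compared with the mean of two (or the reverse, if baseline is the visit with one arm). The result mixes true change with the difference between the patient's arms.

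That difference need not be small. The Background section of the protocol describes asymmetric muscle involvement as common. Inclusion criterion 4 restricts only "screening total RSA (Q1-Q4) without weight in the dominant UE assessed by RWS", so eligibility does not bound the gap between arms.

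The planned analyses do not correct it. The MMRM covariate is the baseline average, which does not carry the arm difference. A one-arm average counts as observed, so Sensitivity Analyses 2 to 4 neither impute it nor count it towards their 10% missing-data trigger. Sensitivity Analyses 1, 5 and 6 address on-treatment data, ranks and strata.

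Baseline is exposed as well: under 9.2, a one-arm Day 1 value could displace a complete two-arm screening value.

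At stake are added noise in the primary endpoint and, if one-arm visits are unbalanced, bias in the treatment difference.

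**Working it through.** **Inputs from the documents (SAP 5).** SD of change 0.08; target difference 0.05; two-sided alpha 0.05; 105 FSHD1 patients per group; 10% missing at Week 48.

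**Assumed inputs.** D, the baseline between-arm difference, from 0.10 to 0.30. f, the share of patients with one arm at Week 48 for a reason other than weakness, from 1% to 10%.

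**Step 1: the plan's own figure.** 105 × 0.9 = 94.5, taken as 94 per group. Noncentral-t power for 0.05 with SD 0.08 is 98.9%, consistent with the stated minimum of 95%.

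**Step 2: one affected visit, no true change.** Let the arms be a (stronger) and b (weaker), with D = a − b. The baseline average is (a + b)/2.

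- Weaker arm missing: a − (a + b)/2 = +D/2.
- Stronger arm missing: b − (a + b)/2 = −D/2.

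Example: arms 0.50 and 0.30 (average 0.40), both unchanged, score +0.10 or −0.10. That is 0.10/0.08 = 1.25 design SDs. D = 0.10 gives 0.05 and D = 0.30 gives 0.15.

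**Step 3: trial level, missing arm random.** The variance of change rises by f × (D/2)². Relative inflation is f × (D/2)²/0.08², and the SD becomes √(0.08² + f × (D/2)²).

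| f | D | Variance inflation | SD | Power, 94 per group |
|---|---|---|---|---|
| 0 | – | 0 | 0.080 | 98.9% |
| 1% | 0.20 | 1.6% | 0.081 | 98.8% |
| 5% | 0.10 | 2.0% | 0.081 | 98.8% |
| 5% | 0.20 | 7.8% | 0.083 | 98.4% |
| 5% | 0.30 | 17.6% | 0.087 | 97.6% |
| 10% | 0.30 | 35.2% | 0.093 | 95.6% |

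A simulation agrees (3,000 trials, Week 48 ANCOVA on baseline, assumed within-patient arm deviation SD 0.04). At D = 0.20, f = 5%, power was 98.1% as written, 98.8% with matched arms, 98.6% requiring both arms, and 98.9% with no one-arm visits. At D = 0.30, f = 10%, the figures were 95.4%, 98.6%, 98.2% and 98.7%. The mean estimate was 0.050 throughout, so there is no bias when one-arm visits are balanced.

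**Step 4: bias under imbalance.** If the weaker arm is the missing one in a share p of cases, the mean shift in a group is f × (2p − 1) × D/2. With f = 5% in both groups, D = 0.20, and p = 0.75 against 0.50, bias = 0.05 × 0.5 × 0.10 − 0 = 0.0025, or 5% of the 0.05 target. The extreme case, one group only and always the same arm, gives f × D/2 = 0.05 × 0.10 = 0.005, or 10% of the target.

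**Step 5: strength, if one arm is accepted.** Illustrative baseline of 2 and 6 kg (average 4); later only the stronger arm is measured, at 5.8 kg. As written: 5.8/4 − 1 = +45.0%. Against the same arm's baseline: 5.8/6 − 1 = −3.3%.

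**The case against.** The strongest reply is that this hardly matters. Both arms are due at every RWS visit, and the main disease-related reason for an untested arm is already set to 0. SAP 9.3.3.1 expects removed sessions to be rare, and removal creates the problem only if a single arm is removed. So f may be well below 5%; at 1% with D = 0.20, power is 98.8%. Power stays above 95% even in the worst case tabulated, and no mechanism is evident for unequal one-arm missingness in a double-blind trial. All of this stands and limits the size of the effect.

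Other mitigations are partial. The by-arm listing in SAP 10.2.1.1 and the exploratory single-arm endpoint recorded in the protocol's summary of changes would expose affected visits, but would not correct the primary value. The rank analysis (Sensitivity Analysis 5) limits the leverage of displaced values without removing them. The strength endpoint is tested by Wilcoxon rank-sum with a planning SD of 46, so a value of +45% acts only through its rank. The strength text may also already exclude one-arm averages.

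SAP 9.3.3.1 also points to a section 9.3.3.3 that is not fully visible in the public text. A further rule there cannot be ruled out, but none is visible.

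**Conclusion.** The point holds and should be fixed. On the visible text, each RSA visit with one arm missing for a reason other than weakness gets a wrong primary-endpoint value. The error is D/2, with sign set by which arm is missing. This follows from the stated rules and needs no assumption about the data.

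The trial-level size does rest on assumptions. For D from 0.10 to 0.30 and f up to 10%, power stays between 98.9% and 95.6%, and balanced one-arm visits cause no bias. Bias needs a difference between groups in how often, or in which arm, data are missing. The trial is not endangered. The case for acting is that the value is wrong where the rule applies, that no planned analysis repairs it, and that choosing a rule after unblinding would be open to challenge. For shoulder strength the defect is ambiguity rather than a definite error.

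**What to change.** In SAP 9.3.3.1, state that 9.3.1.1 does not apply to the two-arm RSA average.

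- **Preferred:** for each visit, after the weakness rule, compute the baseline and visit averages from the arm(s) observed at both times. Keep the two-arm baseline average as the MMRM covariate and say so. Appendix C already works this way for MRI: "if new signal quality issues are identified, the eligible muscle count will change and the Reference Screening values will be updated".
- **Simpler alternative:** set the average to missing unless both arms are present, and let the MMRM handle it.
- **Baseline (9.2):** let a complete two-arm screening value take precedence over a one-arm Day 1 value.
- **Strength (9.3.3.2):** apply the same rule to the two-arm average, then form the relative change. Do not average per-arm relative changes, because that redefines the endpoint: baseline 2 and 6 with follow-up 1 and 6 gives 3.5/4 − 1 = −12.5% as defined, but (−50% + 0%)/2 = −25% per arm. Add a weakness-equals-0 rule only if a reason code is collected for dynamometry.
- **Reporting:** tabulate one-arm visits by treatment group and by which arm was missing.

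The cost is a few sentences, one derivation step and one small table. Results are unchanged wherever both arms are present. The matched-arm rule keeps every visit that has an arm measured at both times. The both-arms rule loses some: ignoring recovery through the MMRM, about 89 per group remain at f = 5% (power 98.6%) and 85 at f = 10% (98.2%). At D = 0.10, f = 5%, that 98.6% is slightly below the 98.8% of the rule as written, which is a reason to prefer matched arms.
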